10.3.3. Validated Investigator’s Global Assessment

The vIGA scale for AD is a 5-point scale to measure disease severity. The IGA score is selected using descriptors that best describe the overall appearance of skin lesions at a given time point using the following scoring: 0 = clear (no inflammatory signs of AD); 1 = almost clear (barely perceptible erythema and papulation); 2 = mild (slight but definite erythema and papulation); 3 = moderate (clearly perceptible erythema and papulation); and 4 = severe (marked erythema papulation) ([vIGA-AD™ 2017](#)). The vIGA will be performed at time points according to the [REDACTED].

10.3.4. Atopic Dermatitis Body Surface Area Involvement

Body surface area affected by AD will be assessed for each section of the body. The possible highest score for each region is: head and neck (9%), anterior trunk (18%), back (18%), upper limbs (18%), lower limbs (36%), and genitals (1%) and will be reported as a percentage of all major body sections combined.

The BSA assessment will be performed at time points according to the [REDACTED].

10.3.5. Patient-Reported Outcomes

10.3.5.1. Pruritus Numeric Rating Scale

The pruritus NRS is a simple assessment tool that subjects will use to report the intensity of their pruritus (itch). The scale for the pruritus NRS is from 0 to 10 with 0 being “no itch” and 10 being “the worst itch imaginable.”

At Baseline and subsequent visits, subjects will be asked to rate the intensity of their itch (maximum/peak and average) over the previous 7 days. Subjects will also be asked to rate their average itch intensity over the previous 24 hours and their maximum itch intensity in a daily diary ([Stander 2013](#), [PruritusResources 2019](#)).

The pruritus NRS will be assessed at time points according to the [REDACTED].

10.3.5.2. Dermatology Life Quality Index

The DLQI is a validated 10-item questionnaire designed to measure the impact of skin disease on the quality of life (QoL) of an affected individual ([Finlay 1994](#)). The format is a simple response to 10 items, which assess QoL over the past week. For each item, the scale is rated as follows: 0 = “not at all”; 1 = “a little”; 2 = “a lot”; 3 = “very much,” with an overall scoring system of 0 to 30; a high score is indicative of a poor QoL. For general inflammatory skin conditions a change in DLQI score of at least 4 points is considered clinically important ([Basra 2015](#)).

The DLQI will be assessed at time points according to the [REDACTED].

10.3.5.3. Patient Global Assessment of Disease

Two questions will be included for subjects to rate their disease and their disease severity.

Subjects will rate their overall well-being based on a 5-point Likert scale from poor to excellent. Subjects will be asked, “Considering all the ways in which your eczema affects you, indicate how well you are doing.” Response choices are: ‘Poor’, ‘Fair’, ‘Good’, ‘Very Good,’ or ‘Excellent’.

Subjects will also be asked to best describe the overall appearance of skin lesions at a given time point using the vIGA scale (Section 10.3.3). The vIGA scale has been adapted for patients to complete. The scale has been modified for easier understanding for subjects, to exclude medical terminology (eg, lichenification has been adapted to thickening and erythema to redness).

Subjects will complete these assessments at time points according to the [REDACTED].

10.3.5.4. Patient Oriented Eczema Measure

The Patient Oriented Eczema Measure (POEM) is a patient-derived validated tool used for monitoring atopic eczema severity. The POEM consists of 7 questions asking patients to rank how many days over the past 7 days they have experienced specific AD-related symptoms ([UON 2004](#), [Charman 2013](#)).

Each of the seven questions carries equal weight and is scored from 0 to 4 as follows: No days = 0; 1-2 days = 1; 3-4 days = 2; 5-6 days = 3; Every day = 4. The scores from the 7 questions are added up to give an overall POEM score. An overall POEM score of 0-2 = 'clear/almost clear', 3-7 = 'mild', 8-16 = 'moderate', 17-24 = 'severe', and 25-28 = 'very severe atopic eczema'.

Subjects will complete these assessments at time points according to the [REDACTED]

[REDACTED]

10.5. Safety Assessments

Planned time points for all safety assessments are provided in the [REDACTED]

10.5.1. Vital Signs

Resting vital sign measurements will be made with the subject in the seated position and include HR, BP, body temperature, respiratory rate. Vital signs will be measured prior to any blood draws that occur at the same study visit or overlapping time point.

10.5.2. Physical Examinations

A complete physical examination will be performed as indicated in the [REDACTED]. A focused physical examination will be performed at all other study visits to assess body systems related to specific areas of complaint (old and new) and for AD severity.

Genitourinary and breast exams may be performed as necessary for assessment of AD severity as needed. Symptom-directed physical examinations may be performed at the investigator's discretion at any time during the study.

The full physical examination includes the following assessments:

- General inspection
- Head/ears/eyes/nose/throat examination
- Neck
- Cardiac examination
- Auscultation of lungs
- Abdominal examination
- Neurological assessment
- Musculoskeletal assessment
- Full skin assessments

[REDACTED]

10.5.4. Clinical Laboratory Assessments

Details regarding clinical laboratory sample collection, preparation, and shipment are provided in the laboratory manual by the central laboratory. All laboratory assessments required by the protocol will be performed by a central laboratory unless otherwise stated. See information on the grading and management of laboratory abnormalities according to assessed severity provided in [Appendix 2](#) and [Appendix 3](#). See [Table 3](#) for the list of clinical laboratory tests to be performed and the [REDACTED] for timing and frequency for each test.

Clinical safety laboratory tests should be completed pre-dose. The investigator must review the laboratory report, document the review, and record any clinically relevant changes on the AE section of the eCRF. The laboratory reports must be filed with the source documents.

All laboratory tests with values considered clinically significantly abnormal during participation in the study, or within 30 days after the last dose of study treatment, should be repeated until the

values return to normal or baseline or are no longer considered clinically significant by the investigator. If such values do not return to normal or baseline, or otherwise resolve to a non-clinically significant value within a reasonable period of time, as judged by the investigator, the etiology should be identified, and the Sponsor should be notified. Relevant local laboratory results and non-protocol specified assessments that are performed at a local laboratory and result in a change in subject management or are considered clinically significant by the investigator (eg, AE or dose modification) should be recorded in the eCRF.

Information on the grading and management of laboratory abnormalities according to assessed severity is provided in [Appendix 2](#) and [Appendix 3](#).

Table 3: Clinical Laboratory Tests

Infectious Disease	Drugs of Abuse
Human immunodeficiency virus (HIV), hepatitis B surface antigen (HBsAg), and hepatitis C virus (HCV) antibody (with reflex PCR) TB with interferon-gamma release assay (IGRA; preferably, QuantiFERON-TB Gold In-Tube).	Urine drug screen: amphetamine, cocaine, methamphetamine, methylenedioxymethamphetamine, or phencyclidine
Pregnancy Testing	Coagulation
Serum pregnancy test human chorionic gonadotropin (β -hCG- [only for females of child-bearing potential with positive urine β -hCG]) Urine β -hCG (only for females of child-bearing potential)	Prothrombin time (PT) Activated partial thromboplastin time (PTT) International Normalized Ratio (INR)
Urinalysis	Hematology
Appearance Bilirubin Color Glucose Ketones Microscopic examination of sediment Nitrite Occult blood pH Protein Specific gravity Urobilinogen	Hematocrit Hemoglobin Mean corpuscular hemoglobin (MCH) Mean corpuscular hemoglobin concentration (MCHC) Mean corpuscular volume (MCV) Platelet count Red blood cell (RBC) count White blood cell (WBC) count with differential [REDACTED]
Serum Chemistry	
Albumin Alkaline phosphatase (ALP) Alanine aminotransferase (ALT) Aspartate aminotransferase (AST) Bicarbonate Blood urea nitrogen (BUN) Calcium Chloride Creatinine with eGFR by CKD-EPI Creatine kinase Gamma-glutamyl transferase (GGT) Glucose Lactate dehydrogenase (LDH)	Lipase Magnesium Phosphorus Potassium Sodium Thyroid-stimulating hormone (TSH) with reflex free T4 and free T3 if abnormal Total bilirubin Direct bilirubin Total cholesterol Total protein Triglycerides Uric acid
Other Tests	
[REDACTED]	

[REDACTED]

[REDACTED]

[REDACTED]

[REDACTED]

[REDACTED]

[REDACTED]

[REDACTED]

[REDACTED]

[REDACTED]

Screening/Baseline Assessment:

The initial eye examination will include:

- Ophthalmologic history

- Best corrected visual acuity measurement (autorefraction, using Snellen chart internationally)
- Ophthalmoscopy (may include contact lens biomicroscopy to examine the macula and optic disc)
- [REDACTED]
- Retinal photographs should be taken
- Ophthalmic findings should be recorded

Post-Screening/Post-Baseline Assessments:

At the scheduled ophthalmology visit, the eye examination will include:

- Ophthalmic history
- Best corrected visual acuity measurement
- Ophthalmoscopy (may include contact lens biomicroscopy to examine the macula and optic disc)
- [REDACTED]
- Retinal photographs should be taken
- Ophthalmic findings should be recorded

Additional testing at the visits should be performed as deemed clinically necessary. Subjects experiencing unexpected ophthalmic symptoms without a known suspected etiology or experiencing a relevant ophthalmic AE may need to have repeat ophthalmoscopy [REDACTED] testing performed. Guidance on clinical monitoring of ophthalmic symptoms is provided in Section 10.5.7.6.

10.5.7. Safety Monitoring Guidance

10.5.7.1. Drug Induced Liver Injury

Based on United States Food and Drug Administration guidance (FDA 2009) for drug induced liver injury, discontinuation of study treatment should be considered if any of the following occur:

- ALT or AST $> 8 \times$ ULN
- ALT or AST $> 5 \times$ ULN for > 2 weeks
- ALT or AST $> 3 \times$ ULN **and** Total Bilirubin $> 2 \times$ ULN, or international normalized ratio > 1.5
- ALT or AST $> 3 \times$ ULN with the appearance of fatigue, nausea, vomiting, right upper quadrant pain or tenderness, fever, rash, and/or eosinophilia ($> 5\%$)

Information on the grading and management of laboratory abnormalities according to assessment severity is provided in Appendix 2 and Appendix 3, respectively.

[REDACTED]

[REDACTED]

[REDACTED]

10.5.7.3. Guidance on Monitoring Subjects for Infections

[REDACTED]

Therefore, investigators and subjects should be vigilant in monitoring for signs and symptoms of infections during the trial and after discontinuation of study treatment. Subjects should be instructed to promptly report to their treating physicians and investigator any signs and symptoms of infection (eg, fever, visualized red or swollen body parts). All infections that develop during the study will be reported as AEs on the respective eCRF pages ([Appendix 2](#)).

All infections that develop during the study will be reported as AEs on the respective eCRF pages. In the case of suspected or confirmed serious or atypical infection that is considered related to study treatment, study treatment interruption should be considered, and the Investigator should inform the medical monitor of any such cases. The elimination half-life of approximately 33 hours allows washout of etrasimod within a week.

Additional evaluations will be performed at the discretion of the Investigator and/or specialist consultants.

[REDACTED]

All radiologic images (eg, magnetic resonance imaging, computer tomography, x-rays) and diagnostic laboratory test results performed by local laboratories/facilities should be retained as source documents by study sites and made available upon request by the Sponsor for central adjudication as needed. All infections that develop during the study will be reported as AEs on the respective eCRF pages.

The Investigator should consider early treatment with specific antimicrobial therapy on the basis of clinical diagnosis or suspicion thereof (eg, antiviral treatment for herpes simplex or zoster) and may consult with infectious disease experts, as appropriate.

[REDACTED]

[REDACTED]

[REDACTED]

[REDACTED]

- [REDACTED]
- [REDACTED]
- [REDACTED]
- [REDACTED]
- [REDACTED]

[REDACTED]

[REDACTED]	[REDACTED]	[REDACTED]	[REDACTED]
[REDACTED]	[REDACTED]	[REDACTED]	[REDACTED]
[REDACTED]	[REDACTED]	[REDACTED]	[REDACTED]
[REDACTED]	[REDACTED]	[REDACTED]	[REDACTED]

[REDACTED]

- [REDACTED]

[REDACTED]

[REDACTED]
[REDACTED]
[REDACTED]
[REDACTED]

[REDACTED]

[REDACTED]

[REDACTED]

[REDACTED]

- [REDACTED]
- [REDACTED]
- [REDACTED]

- [REDACTED]

[Redacted text block]

[Redacted]
[Redacted]
[Redacted]

[Redacted text block]

[Redacted text block]

[Redacted text block]

[Redacted text block]

[REDACTED]

10.5.7.6. Ophthalmic Symptom Monitoring

[REDACTED]

Subjects experiencing unexpected ophthalmic symptoms, including blurred vision, decreased visual acuity, or other clinically significant ocular adverse events, without a known/suspected etiology may need to have repeat ophthalmoscopy [REDACTED] testing performed. [REDACTED]

[REDACTED]

Unscheduled ophthalmology visits in case of any visual complaint: If, during the study, there are complaints of decreased vision or identification of worsening visual acuity (equal to or more than 2 lines on a standard eye chart using best corrected vision) then an unscheduled ophthalmic examination should be performed.

At an unscheduled ophthalmology visit, the eye examination will include:

- Best corrected visual acuity measurement
- Ophthalmoscopy (may include contact lens biomicroscopy to examine the macula and optic disc)

[REDACTED]

[REDACTED] These subjects must be followed up monthly with ophthalmologic evaluations until such time as resolution is confirmed or no further improvement is expected by the ophthalmologist (based on a follow-up period of not less than 3 months). These evaluations will include repeat best-corrected visual acuity, fundus examination, [REDACTED]. If the subject does not show definite signs of improvement on examination by specialist testing [REDACTED] 6-8 weeks after interruption of study treatment, then therapy for macular edema in conjunction with an ophthalmologist experienced in the management of this condition should be initiated.

[REDACTED]

10.5.8. Adverse Events

10.5.8.1. Definitions

10.5.8.1.1. Adverse Event

An AE is any untoward medical occurrence that does not necessarily have a causal relationship with this treatment. An AE can therefore be any unfavorable and unintended sign, symptom, or disease temporally associated with the use of a medicinal product, whether or not considered related to the medicinal product.

AEs can include, but are not limited to, any of the following:

- Unfavorable changes in general condition
- Subjective or objective signs/symptoms
- Concomitant disease or accidents
- Clinically relevant adverse changes in laboratory parameters over the course of the study
- Pre-existing conditions that worsen in severity, increase in frequency, or have new signs/symptoms

Information on the grading and management of laboratory abnormalities according to assessment severity is provided in [Appendix 2](#) and [Appendix 3](#), respectively.

10.5.8.1.2. Serious Adverse Event

An AE should be classified as a serious adverse event (SAE) if it meets 1 of the following criteria:

Fatal:	The AE resulted in death.
Life-threatening:	The AE placed the subject at immediate risk of death. This classification does not apply to an AE that hypothetically might cause death if it were more severe.
Hospitalization:	The AE required or prolonged an existing inpatient hospitalization. Hospitalizations for elective medical or surgical procedures or treatments planned before the signing of informed consent in the study or routine check-ups are not SAEs by this definition.
Disabling/ incapacitating:	The AE resulted in a persistent or significant incapacity or substantial disruption of the subject's ability to conduct normal life functions.
Congenital anomaly or birth defect:	An adverse outcome in a child or fetus of a subject exposed to the study treatment before conception or during pregnancy.
Medically significant:	The AE did not meet any of the above criteria but could have jeopardized the subject and might have required medical or surgical intervention to prevent one of the outcomes listed above or involves suspected transmission via a medicinal product of an infectious agent.

10.5.8.1.3. Adverse Drug Reaction

An adverse drug reaction (ADR) in the pre-approval clinical experience with a new medicinal product or its new usages, particularly as the therapeutic dose(s) may not be established, is any noxious and unintended response to a medicinal product related to any dose. The phrase “responses to a medicinal product” means that a causal relationship between a medicinal product and an AE is at least a reasonable possibility (ie, the relationship cannot be ruled out).

10.5.8.1.4. Events of Interest

Based on the mechanism of action of etrasimod and prior experience with other agents acting via a similar mechanism, as well as known comorbid conditions with AD, potential events of interest may be identified. In addition to appropriate reporting of these events as an AE or an SAE, supplementary detailed information may be collected.

10.5.8.1.5. Severity

The severity of each AE will be assessed at the onset by a nurse/or physician. When recording the outcome of the AE, the maximum severity of the AE experienced will also be recorded. The severity of each AE will be graded according to the Common Terminology Criteria for Adverse Events:

Grade 1	Mild; asymptomatic or mild symptoms; clinical or diagnostic observations only; intervention not indicated.
Grade 2	Moderate; minimal, local or noninvasive intervention indicated; limiting age-appropriate instrumental activities of daily living.
Grade 3	Severe or medically significant but not immediately life-threatening; hospitalization or prolongation of hospitalization indicated; disabling, limiting self-care activities of daily living (eg, preparing meals, shopping for groceries or clothes, using the telephone, managing money).
Grade 4	Life-threatening consequences, urgent intervention indicated.
Grade 5	Death related to an AE.

Additional information on CTCAE grading of AEs is provided in [Appendix 2](#).

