APPENDIX 2: GRADING OF CLINICAL AND LABORATORY ADVERSE EVENTS

All clinical and clinically significant laboratory abnormalities will be graded according to the CTCAE Scale for Severity of Adverse Events and Laboratory Abnormalities (available at: https://ctep.cancer.gov/protocoldevelopment/electronic_applications/docs/ctcae_v5_quick_reference_5x7.pdf).

Examples of CTCAE terms and grading are provided for clinical adverse events in [Table 10](#) and for laboratory abnormalities in [Table 11](#).

Table 10: Example of CTCAE Terms and Grading for Clinical Adverse Events

Respiratory, thoracic and mediastinal disorders					
CTCAE Term	Grade 1	Grade 2	Grade 3	Grade 4	Grade 5
Cough	Mild symptoms; nonprescription intervention indicated	Moderate symptoms; medical intervention indicated; limiting instrumental ADL	Severe symptoms; limiting self-care ADL	–	–
Definition: A disorder characterized by sudden, often repetitive, spasmodic contraction of the thoracic cavity, resulting in violent release of air from the lungs and usually accompanied by a distinctive sound.					
Dyspnea	Shortness of breath with moderate exertion	Shortness of breath with minimal exertion; limiting instrumental ADL	Shortness of breath at rest; limiting self-care ADL	Life-threatening consequences; urgent intervention indicated	Death
Definition: A disorder characterized by an uncomfortable sensation of difficulty breathing.					
Wheezing	Detectable airway noise with minimal symptoms	Moderate symptoms; medical intervention indicated; limiting instrumental ADL	Severe respiratory symptoms limiting self-care ADL; oxygen therapy or hospitalization indicated	Life-threatening consequences; urgent intervention indicated	Death
Definition: A disorder characterized by a high-pitched, whistling sound during breathing. It results from the narrowing or obstruction of the respiratory airways.					
Dizziness	Mild unsteadiness or sensation of movement	Moderate unsteadiness or sensation of movement; limiting instrumental ADL	Severe unsteadiness or sensation of movement; limiting self-care ADL	–	–
Definition: A disorder characterized by a disturbing sensation of lightheadedness, unsteadiness, giddiness, spinning or rocking.					

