- TEAEs by SOC, PT, and maximum Common Terminology Criteria for Adverse Events (CTCAE) severity
- TEAEs by SOC, PT, and maximum relationship to the study treatment
- Non-serious TEAE by SOC and PT

Targeted Medical Events by PT and Category will be summarized for DB Treatment Period, OLE Period, and overall.

All AEs will be presented in a by-treatment, and by-subject listing, for the DB treatment and OLE Periods separately, detailing the verbatim term given by the investigator, the PT, SOC, onset date, end date, CTCAE grade, outcome, relationship to study treatment, action taken with study drug, other action taken, seriousness and criteria for seriousness. SAEs and AEs leading to study treatment discontinuation will also be presented in a separate listing.

D. Clinical Laboratory Results

Laboratory parameters from the central laboratory will be summarized by treatment group at each scheduled assessment time point. For continuous lab parameters (hematology, serum chemistry, coagulation, and urinalysis), absolute values and change from Baseline will be summarized using descriptive statistics. For the OLE Period, change from Baseline will be calculated for the DB baseline and OLE baseline separately. Associated laboratory parameters (e.g., hepatic

[REDACTED]

enzymes, renal function, and hematology) will be grouped and presented together.

Changes from Baseline in the out of reference range abnormality flags will also be summarized using shift tables at each post-Baseline visit.

Data listings by-treatment and by-subject will be provided for all laboratory parameters reported in the standard units provided by the central laboratory. Lab values outside of the standard reference range will be noted.

Local laboratory assessments will be displayed in a separate listing. Pregnancy test results will be listed.

E. Vital Signs

Descriptive statistics for absolute values and change from Baseline in vital signs (BP, HR, respirations, body temperature) will be presented by treatment group. For OLE Period, change from Baseline will be calculated for the DB baseline and OLE baseline separately.

At baseline and week 16, descriptive statistics for pre-dose measurements and change of vital signs values will be presented by treatment group [REDACTED] after treatment initiation. [REDACTED]

[REDACTED]

[REDACTED]

[REDACTED]

[REDACTED]

[REDACTED]

[REDACTED]

[REDACTED]

[REDACTED]

[REDACTED]

G. Physical Examination

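### Protocol 10.5.8.1.5 puts instrumental-activity examples on the Grade 3 self-care line, so a clinical AE graded on activity limitation can be read as Grade 2 or Grade 3

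*Protocol*

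**What the plan says.** Protocol 10.5.8.1.5 names the scale: "The severity of each AE will be graded according to the Common Terminology Criteria for Adverse Events". It then prints a general description of each grade. The activity criterion at Grade 2 is "limiting age-appropriate instrumental activities of daily living", with no examples. At Grade 3 it is "limiting self-care activities of daily living (eg, preparing meals, shopping for groceries or clothes, using the telephone, managing money". The section closes by sending the reader on: "Additional information on CTCAE grading of AEs is provided in" Appendix 2.

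Appendix 2 states that "All clinical and clinically significant laboratory abnormalities will be graded according to the CTCAE Scale for Severity of Adverse Events and Laboratory Abnormalities", links the CTCAE version 5 quick reference, and gives sample rows. The cough row has "Moderate symptoms; medical intervention indicated; limiting instrumental ADL" at Grade 2 and "Severe symptoms; limiting self-care ADL" at Grade 3.

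Grades feed the safety reporting. Protocol 11.8.1 lists AE severity among the safety endpoints, Protocol 11.8.2 summarises TEAEs by severity, and SAP 9.C tabulates "TEAEs by SOC, PT, and maximum Common Terminology Criteria for Adverse Events (CTCAE) severity" for the double-blind period, the open-label extension and overall.

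**The concern.** Preparing meals, shopping, telephoning and handling money are practical household tasks. They are not care of one's own body. They illustrate the Grade 2 term but are printed under the Grade 3 term. A rater who follows the term and a rater who follows the examples can give the same event different grades. The difference runs one way: following the examples lifts a Grade 2 event to Grade 3.

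The boundary matters because Grade 3 is where the scale begins to call an event severe. Protocol 10.5.8.1.5 lets a nurse or a physician grade, and the trial is multicentre, so different raters may settle the conflict differently. What is at stake is how far the severe-AE proportions can be relied on, mainly their absolute level. That applies especially to the 52-week extension, where every subject receives 2 mg and the analysis is descriptive, with no concurrent control.

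**Working it through.** The plan states no expected Grade 2 or Grade 3 rate, so there is no figure to reproduce. The check is a comparison of texts.

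| Source | Grade 2 activity limit | Grade 3 activity limit | Examples |
|---|---|---|---|
| Protocol 10.5.8.1.5 | instrumental | self-care | Grade 3 only: meals, shopping, telephone, money |
| Appendix 2, Table 10 (cough, dyspnea, dizziness, blurred vision) | instrumental | self-care | none |

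1. Both places use the same split, so the intended boundary is clear: instrumental is Grade 2 and self-care is Grade 3.
2. Neither place defines the two terms. The list in 10.5.8.1.5 is the only explanation of self-care in the protocol's printed text. A rater using Appendix 2 who asks what self-care means would be led to that list.
3. Take an event whose only effect is that the subject cannot shop. By the term it is Grade 2 in both places. By the examples it is Grade 3. The two readings cannot both be right.
4. The conflict bites only where activity limitation decides the grade. Dizziness in Table 10 is such a row: apart from moderate versus severe unsteadiness, the type of activity is the only criterion. The ALT and AST rows in Table 11 use numerical limits and cannot be affected.

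**Scale of a shift.** The planned size is 40 subjects per arm (Protocol synopsis). One subject moved from a maximum of Grade 2 to Grade 3 changes that arm's proportion by 1/40 = 2.5 percentage points.

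**Assumed range, for illustration only.** Suppose 10% to 30% of an arm has a maximum Grade 2 TEAE that was graded on activity limitation, and 10% to 100% of those subjects are moved up by the examples.

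- Low: 40 × 0.10 × 0.10 = 0.4 subjects; 0.4/40 = 1 percentage point.
- High: 40 × 0.30 × 1.00 = 12 subjects; 12/40 = 30 percentage points.

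If raters ignore the list, the shift is zero. None of these rates is in the documents. A range this wide shows only that the size cannot be determined from them.

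**The case against.** The strongest reply is that the list is an aside in a general summary. The governing scale is CTCAE, the section refers raters to Appendix 2, and Appendix 2 gives term-specific rows without the examples and links the full reference. Grades 2 and 3 also carry other criteria, such as the intervention needed, hospitalization and medical significance, and these will settle many grades. This stands as mitigation and narrows the set of events affected. It does not remove the conflict: 10.5.8.1.5 is operative grading text that presents its own lines as the CTCAE grades, and Appendix 2 leaves both terms undefined.

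A second reply is that the consequences are limited, and this stands. Grading in the double-blind period is masked, so the wording alone gives no reason for one arm to be upgraded more than another. SAE classification and the 24-hour report depend on seriousness, not on grade (Protocol 10.5.8.1.2 and 10.5.8.3.1). Masking does not protect absolute Grade 3 proportions, and it does not apply in the open-label extension.

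A reader might infer that severe AEs are in fact over-counted, and unevenly across sites. The documents do not support that, because nothing in them shows how any site graded. A reader might also infer that the wording alters AE management through Appendix 3. The grade-specific rules in its printed text concern laboratory abnormalities, which do not turn on daily activities. The guidance for clinical AEs is in a figure that is not shown, so no such effect can be verified.

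**Conclusion.** The concern holds as an internal contradiction that is wrong as written. The Grade 3 examples in Protocol 10.5.8.1.5 describe the Grade 2 category of the same section and of Appendix 2. This puts the severity tables at risk of upward and inconsistent grading for clinical AEs whose grade turns on activity limitation.

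The size is unknown and may be near zero, and no single figure for an over-count can be defended. The judgement rests on the ordinary meaning of the two activity terms and on the protocol's own split between them, because the documents define neither. No efficacy result, error rate, power or sample size is affected.

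**What to change.** - Move the parenthesis on meals, shopping, telephone and money to the Grade 2 line of Protocol 10.5.8.1.5.
- Define instrumental and self-care activities once, and reconcile that section with Appendix 2 and the CTCAE version it cites. Any self-care examples should come from that version, because Appendix 2 contains none.
- Send sites a short memo on the change.

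The cost is a brief protocol clarification and the memo.

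If AEs already graded are reviewed, the review should be blinded to treatment and cover Grade 2 and Grade 3 alike. A query of Grade 3 events alone could only lower grades and would add a bias of its own. Such a review would also cost more than a listing: the AE eCRF items in Protocol 10.5.8.2.2 record severity but not the reason for the grade, so the affected events cannot be picked out from those fields and would need source review. Blinding needs deliberate arrangement, because SAP Section 12 already gives subject counts by treatment group, which suggests that assignments are known to those preparing the analyses.
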